Methods. A parallel cluster randomized trial (with baseline-line measurements) across 20 National Health Service (NHS) hospitals in England. The hospitals will be randomly split into two groups. One group will be scheduled to experience the training intervention, and the other group will be placed on a waiting list to experience the training later. The primary analysis will compare the difference in the use of indicated control charts between waitlist control and intervention hospitals (adjusting for pre-intervention use) reported with 95% confidence intervals. A qualitative thematic analysis of feedback forms will be conducted.

Discussion. The present research will evaluate the impact of the training intervention on the use of control charts. The results will apply to institutions that are non-early adopters of this training intervention.

Keywords: Quality Improvement, Data Visualisation, Change Management, Learning Health System, Inservice Training

INTRODUCTION/BACKGROUND

Problem description

The way data are presented can influence board members' decisions.² Statistical process control (SPC) charts provide a data-driven approach to guide decisions related to quality improvement.^{3,4} A previous study demonstrated that SPC charts are seldom used in National Health Service (NHS) hospital board papers in England,^{5,6} and inspired an NHS-Improvement/England (NHS I/E) (2019) initiative called 'Making Data Count.' Making Data Count aims to help NHS staff create and use SPC charts effectively.⁷ Starting in late 2017 this training was offered on a first-come, first-serve basis. As of April 2021, approximately 120 organizations have taken part. A non-randomized retrospective evaluation suggests that the training may be effective for early adopters,^{8,9} but whether these benefits extend to hospitals less eager to take part is uncertain.

NHS-Improvement's team reviewed published board papers for every hospital in England in 2020 (at the time 217) to determine what presentation format was predominately used in their board papers to present quality and safety metrics. Seventy-five hospital board papers lacked SPC charts. Rather, these board papers were predominantly composed of Red-Amber-Green (R-A-G) data presentations or two-point comparisons, e.g., year 1 vs year 2, neither of which are data-driven presentation methods for quality improvement.¹⁰

Available knowledge

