Based on our sample size calculation, a minimum of 16 hospitals with pre- and post-intervention measures is required to detect a 30-percentage point increase in the proportion of indicated SPC charts from 10% to 40% between control and intervention measures. The sample size was calculated with an alpha of 0.05 and a power of 0.80. Due to the study design (measurements taken of the outcome in a baseline period), adjustment for the correlation between pre- and post-intervention measures were made, estimated at $r=0.90$.³¹ The primary analysis will be conducted based on intention-to-treat. While only 16 hospitals are required, we have planned to include 20 on an ‘insurance principle’ in case some hospitals drop out.

Selection and randomization of hospitals

At the present time, SPC training cannot be mandated. The hospitals that take part will ultimately depend on their willingness and availability to experience training. The five-step selection and randomization process for hospitals is presented in Figure 3. **Step 1** involves obtaining contact information for all the hospitals identified as relying on R-A-G charts or two-point comparisons to present quality and safety performance metrics in their board papers (75 at the time the protocol is being written). **Step 2** involves the Making Data Count team inviting the hospitals to take up training over a specified 12-month period. As part of their informed consent, hospitals will be made aware that they may be offered training over either the initial 6-months or the later 6-months in a randomized fashion. **Step 3** involves selecting the 20 hospitals that first express an interest in taking up the training or a smaller number which do so after 30 days have passed (note that recruitment will continue until 20 express an interest – see Step 5). The Making Data Count team will email the list of

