Step 2: R1 will take a screenshot of each quality and safety chart and the supporting text, removing identifying features, e.g., the name of the hospital and/or calendar dates, and send the redacted charts to R3 and R4. A screen shot of the supporting text will be taken, also removing identifying features.

Step 3: R3 and R4 will independently code features of the charts and supporting texts, which are described in Table 4.

Table 4. Step 4 coded elements

Extracted item to be coded	Code Name	Explanation
Quality and Safety Charts	Chart type	whether the chart is a time series chart, between subjects chart, time and between chart, or other (e.g., pie). The categories will be exclusive, such that only one may be selected.
Quality and Safety Charts	SPC?	whether the chart is a SPC chart (yes/no)
→If “yes” to SPC? then the following elements are also coded		
Quality and Safety Charts SPC Charts	Recalculations	whether the control limits are recalculated (yes/no)
Quality and Safety Charts SPC Charts	Special Cause Highlights	whether any data are highlighted as special cause (yes/no)
	...Special Cause Highlights-as recommended	and if “yes” whether the recommended blue/orange colors are used (yes/no)
Quality and Safety Charts SPC Charts	R-A-G ³	whether any data are highlighted as R-A-G colors (yes/no)
	...R-A-G as NOT recommended	and if “yes” whether those R-A-G colors follow the former performance-based target model of data monitoring (yes/no)
Quality and Safety Charts SPC Charts	Labels	whether there are labels on the chart describing where process labels are set (yes/no)
	...Labels	and if “yes” AND are the labels different from “3-sigma” (yes/no)
Supporting text	Explaining where control lines are set	whether the text explains where the control lines are set (yes/no)
Supporting text	Reasons for variations	whether the text posits reasons for variation (yes/no)
Supporting text	Suggestions for improvements	whether the text suggests interventions (yes/no)

³ Making Data Count trainers believe it is valuable to extract data about whether RAG colorings continue to be used for at least two reasons. First, RAG colors are predominantly used by the trust being invited to attend the training. Second, the training intervention explicitly informs attenders that RAG presentations are not well suited to quality improvement methodologies and urges attenders to move away from RAG presentations towards SPC presentations.

Blinding and agreement

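### R-A-G coloring is coded only on charts already classed as SPC, so the plan cannot show whether R-A-G coloring continues to be used

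*Combined protocol and SAP*

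**What the plan says.** All references are to the combined protocol and SAP.

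- **Data extraction from board papers, Table 4.** Two items are coded on every quality and safety chart: chart type and whether the chart is SPC. The rest of the chart items come after a condition: on a yes, "to SPC? then the following elements are also coded". The R-A-G item ("whether any data are highlighted as R-A-G colors (yes/no") and its follow-up, on whether the colors follow the former target model, stand below that condition. The R-A-G row carries the same SPC-chart label as the rows on recalculated limits and process labels.
- **Footnote 3 to Table 4.** The trainers want to know if R-A-G coloring persists. They give two reasons: the invited trusts predominantly use it, and the training "urges attenders to move away from RAG presentations towards SPC presentations".
- **Problem description.** In the 2020 review, "Seventy-five hospital board papers lacked SPC charts".
- **Selection and randomization of hospitals.** Invitations go to hospitals "identified as relying on R-A-G charts or two-point comparisons to present quality and safety performance metrics in their board papers".
- **Step 2 of data extraction.** "R1 will take a screenshot of each quality and safety chart and the supporting text", and the redacted images go to the blinded coders R3 and R4.
- **Analysis of data from board papers.** Outcomes other than the main one, R-A-G among them, are reported descriptively.

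**The concern.** The R-A-G item is conditioned on the behavior that the training tries to change. A chart enters the R-A-G record only once it has become an SPC chart. The hospitals were invited because they relied on R-A-G or two-point comparisons, so their baseline R-A-G use lies largely where the item does not look.

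The item as placed answers a narrow question: do SPC charts carry R-A-G colors? Footnote 3 asks a wider one. A count or percentage built from the narrow item and read as an answer to the wider one could mislead. It would start at or near zero before training and in untrained waitlist hospitals, and could rise only where SPC charts appear.

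**Working it through.** **The plan's own figure.** The sample size section states that "a minimum of 16 hospitals with pre- and post-intervention measures is required", for a "30-percentage point increase in the proportion of indicated SPC charts from 10% to 40% between control and intervention measures", with r = 0.90. A two-sided, continuity-corrected comparison of 10% with 40% at 80% power needs 38 per arm. Multiplying by 1 − 0.90² = 0.19 gives 7.22, rounded up to 8 per arm, or 16 in total. The figure reproduces and is not in dispute. Only the planning values 10% and 40% are used below.

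**Step 1: which charts get an R-A-G code.**

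| Chart | Chart type | SPC? | R-A-G and follow-up |
|---|---|---|---|
| Full chart, SPC | coded | coded | coded |
| Full chart, not SPC | coded | coded | not coded |

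The chart-type categories concern time series, between-subjects comparison, both, or other. None identifies R-A-G, so it cannot be recovered from another item.

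**Step 2: share of full charts with no R-A-G record.** Let s be the share of full quality and safety charts that are SPC. The uncoded share is 1 − s.

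- s = 0: 1 − 0 = 100%
- s = 0.10: 1 − 0.10 = 90%
- s = 0.40: 1 − 0.40 = 60%

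The planning values describe indicated charts, which include unique icons, so the 90% and 60% assume no icons. With M full charts and k counted icons, the outcome is p = (sM + k)/(M + k), so s = p − (1 − p)k/M. Any icons put s below p. The uncoded share is therefore at least 90% when p = 10% and at least 60% when p = 40%. For example, at p = 40%, k = M/6 gives s = 0.40 − 0.60/6 = 0.30, so 70% is uncoded; k = M/3 gives s = 0.20, so 80% is uncoded.

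**Step 3: can the record move the wrong way?** The documents give no chart counts, so these are assumed for illustration. A paper has 20 full charts, all non-SPC and all R-A-G colored. After training, 8 become SPC, of which 2 keep R-A-G colors; of the other 12, 4 stay R-A-G.

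| | Before | After |
|---|---|---|
| True R-A-G charts | 20 of 20 (100%) | 2 + 4 = 6 of 20 (30%) |
| Recorded R-A-G charts | 0 | 2 |
| Recorded share of SPC charts | 0/0, undefined | 2/8 (25%) |

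True use falls by 14 charts while recorded use rises by 2. If a waitlist paper stays at 20 non-SPC R-A-G charts, its record is 0. The trained hospital then appears to have 2 more R-A-G charts than the untrained one, when it has 20 − 6 = 14 fewer.

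**The case against.** The strongest defense is that the SPC-only item is coherent in itself. It sits beside the item on the recommended highlight colors, and its follow-up asks whether the old target-based coloring has been carried over. On that reading it checks the quality of new SPC charts, and footnote 3 merely explains the trainers' interest. This stands in part: the narrow question is legitimate and worth keeping. But the footnote's reasons rest on R-A-G use in hospitals whose papers lacked SPC charts in 2020, and an item blind to non-SPC charts cannot speak to that.

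Three further points stand. R-A-G is a descriptive secondary item. The documents do not say how much R-A-G appears in charts and how much in tables, so recoding charts is a partial remedy. And some hospitals may have begun using SPC charts since 2020, so the baseline record need not be empty everywhere.

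A reader might infer that the plan cannot detect a move towards SPC. It can: SPC status is coded on every quality and safety chart and feeds the primary outcome. The gap is confined to R-A-G on charts that are not SPC.

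A reader might also infer that the primary outcome needs a required analysis on full charts only, because R1 and R2, who are not blinded, judge which icons count. The documents do not support that as a necessary change. Icons are taught as a way to summarize control charts left out of the paper, and they count by deliberate definition. Uniqueness rules, double coding and agreement statistics are planned, the split between icons and full charts will be described, and the blinding limit is disclosed. Removing icons would change the quantity estimated while R1 and R2 still selected the charts, so it could not separate coder bias from icon use as trained. For scale, with assumed errors: in a paper scoring 12/30 = 40% with 10 icons, wrongly counting 1, 2 or 3 of them means true values of 11/29 = 37.9%, 10/28 = 35.7% or 9/27 = 33.3%. That is an overstatement of 2.1, 4.3 or 6.7 points against a 30-point design effect. Such an analysis is optional.

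**Conclusion.** The point holds as a mismatch between the reach of the R-A-G item and the purpose in footnote 3. No R-A-G record exists for a paper without SPC charts, and 90% of full charts go uncoded at 10% SPC if there are no icons. Because the recorded charts are selected by the outcome of training, R-A-G as coded cannot validly be compared over time or between arms, and it may move opposite to true use.

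The shares in Step 2 follow from the coding rule and the planning values. The reversal in Step 3 rests on assumed counts: it shows what can happen, not what will. The primary outcome, its test and the sample size are unaffected. This is a cheap improvement to a descriptive secondary outcome.

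**What to change.** In Table 4, place the R-A-G item and its follow-up above the SPC condition, and label them as applying to all quality and safety charts, so that R3 and R4 code them at both time points. Report R-A-G separately for SPC and non-SPC charts; this keeps the narrow question and answers the wider one. State that R-A-G in tables not extracted as charts remains unmeasured.

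The cost is one additional yes/no code by each of R3 and R4, plus the follow-up where it applies, on every non-SPC chart. On the shares above, that is most of the charts. They already receive these screenshots, so no new extraction is needed, and the coding would be done by the blinded pair. Narrowing footnote 3 instead would remove the mismatch on paper but leave the trainers' question unanswered.

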Figure 5. Selected board papers retrieved from each hospital during the pre-intervention intervention and post intervention observation periods

Notes: The top box depicts the trusts that will experience the intervention (the intervention group), and the bottom box depicts trusts that will be placed on a waiting list to experience the intervention later (the control group). The black cells show the month of the training intervention. Green cells represent the month from which the pre-intervention papers will be retrieved, and the red cells represent the month from which the post-intervention papers will be retrieved.

For hospitals in the waitlist control group, we will form a matched list based on the order in which each is scheduled to receive training (earliest month) under the waitlist design. For example, the hospital in the intervention group scheduled to receive training first will be matched with the hospital in the waitlist group scheduled to receive training first, see the bottom half of Figure 5. This ordering is planned to minimize the possibility for waitlist hospitals to experience the training in the timespan planned for the current evaluation the waitlist control group's "post-observation" board papers will be selected from a month before each waitlist control hospital experiences training.

Outcome measures²

² The outcome measures were informed by the previous non-randomized studies discussed in the problem section and through conversations with trainers who designed the Making Data Count intervention.

Our data will be made publicly available for replication and further analyses. The main outcome measure will be the proportion of SPC charts indicated about quality and safety measures (the numerator) out of all quality and safety charts indicated in the board papers (the denominator). SPC icons will be added to the numerator and the denominator where they indicate that a unique control chart has been used but not included in the paper. Additional secondary outcome measures will be extracted from the board papers and feedback forms, as described below.

Data extraction from board papers

Quantitative measures for data contained in the board papers will be created by coding information within each board paper. Four independent reviewers (R1, R2, R3, R4) will conduct the coding over three steps.

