Step 1: R1 will download the papers. From each paper, R1 and R2 will independently extract the following three types of items: (A) the charts that appear, (B) SPC icons that appear indicating a control chart has been used, and (C) any supporting text aside charts that appear as instructed by the Making Data Count training, see Figure 1. They will then independently code aspects of the extracted charts and icons as described in Table 3.

Table 3. Step 1 coded elements.

Extracted item to be coded	Code Name	Explanation													
Charts	Quality and Safety-Chart	whether the chart is about a quality or safety measure (yes/no)													
SPC Icons	Quality and Safety-Icon	whether the icon is about a quality or safety measure (yes/no)													
→ If “yes” to Quality and Safety-Icon, then the following element also coded															
Quality and Safety SPC Icons	Icon indicating unique SPC chart	whether the SPC icons indicates a unique chart (yes/no) – a “yes” response indicates that this icon is added to the total numbers of control charts (numerator) and charts (denominator)													
Quality and Safety SPC Icons	Icon – Purpose	whether the SPC icon is being presented for “assurance” purposes or to convey information about process “variation” 
  
 Variation	Assurance	
   
 							
  
	Variation			Assurance									
Variation			Assurance												

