Quality and Safety SPC Icons	Icon – Information	whether the SPC icon indicates common cause, special cause of a concerning nature, special cause of an improving nature, inconsistently hitting the target, consistently passing the target, or consistently failing the target 
  
 Common cause – no significant change	Special cause of concerning nature or higher pressure due to (H)higher or (L)lower values	Special cause of improving nature or lower pressure due to (H)higher or (L)lower values	Variation indicates inconsistently passing and failing short of the target	Variation indicates consistently (P)assing the target	Variation indicates consistently (F)ailing short of the target	
   
 						
  
	Common cause – no significant change	Special cause of concerning nature or higher pressure due to (H)higher or (L)lower values	Special cause of improving nature or lower pressure due to (H)higher or (L)lower values	Variation indicates inconsistently passing and failing short of the target	Variation indicates consistently (P)assing the target	Variation indicates consistently (F)ailing short of the target							
Common cause – no significant change	Special cause of concerning nature or higher pressure due to (H)higher or (L)lower values	Special cause of improving nature or lower pressure due to (H)higher or (L)lower values	Variation indicates inconsistently passing and failing short of the target	Variation indicates consistently (P)assing the target	Variation indicates consistently (F)ailing short of the target										

SPC icons will not be extracted that simply inform the reader what they stand for, e.g., the legend in Figure 2a. The coded element named “Indicating unique SPC chart” reflects that when multiple icons refer to the same SPC chart only one SPC chart will be counted as unique, see Figure 6. Where an icon appears along with the SPC chart it represents, it will not be counted as unique, see Figure 7.

Figure 6. Example of two icons appearing together about the same SPC chart.

[figure not shown]
[figure not shown]

Figure 7. Example of an SPC icon appearing with the SPC chart it represents.

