Initially, codes will be independently assigned. Disagreements will be resolved through consensus discussions. Any disagreements that cannot be resolved will be referred to the chief investigator. It is not possible to blind reviewers R1 and R2 to the board papers group or time-period, as they are extracting charts from the published board papers. R3 and R4 will be blinded and will be instructed to inform R1 if they are unblinded to experimental group at any point, and whether/how often they are unblinded will be reported in the final manuscript.

Data extraction from feedback forms

Data extracted from feedback forms will include trainees' Likert ratings and free-text responses, see Table 2. These data will be compiled into an Excel file. R1 and R2 will independently code whether each free-text response is positive (e.g., "The training was practically useful."), negative (e.g., "The training went so fast that I couldn't keep up."), or neutral (e.g., "Handouts provided.").

Planned Analyses*Analysis of data from board papers*

The hospitals will be described according to how many days it took them to accept the training invitation, along with their size (number of beds), and local deprivation status, as indicated on NHS Digital's Peer Finder Tool.³³ The inter-rater reliability of the data extracted from the board papers will be calculated using Kappa statistics and percentage agreement to quantify the level of agreement between reviewers. Descriptive statistics will enumerate the proportion of control charts that show the full detail and those appearing as icons.

The main analysis will examine the effect of the training intervention. For each hospital, we will observe the proportion of indicated SPC charts, including SPC icons, about quality and safety measures (the numerator) out of all quality and safety charts indicated in

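### Only one of the four codes behind the main outcome is assigned blind, and chart eligibility could be moved to the blinded coders at little cost

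*Combined protocol and SAP*

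**What the plan says.** Under Outcome measures, the main outcome is SPC charts on quality and safety divided by all quality and safety charts indicated. Icons count as well: "SPC icons will be added to the numerator and the denominator where they indicate that a unique control chart has been used".

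Data extraction from board papers splits the coding in two.

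- **Step 1, Table 3 (R1 and R2).** After extraction, "They will then independently code aspects of the extracted charts and icons as described in Table 3". The table holds three codes that enter the main outcome: whether a chart concerns quality or safety, whether an icon does, and whether an icon stands for a unique chart. The text after Table 3 gives rules for uniqueness, for example: "Where an icon appears along with the SPC chart it represents, it will not be counted as unique".
- **Steps 2 and 3, Table 4 (R3 and R4).** "R1 will take a screenshot of each quality and safety chart and the supporting text", with identifying features removed, and sends the charts on. R3 and R4 code chart type, SPC status, SPC features and supporting text. Only SPC status enters the main outcome.

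Blinding and agreement states: "It is not possible to blind reviewers R1 and R2 to the board papers group or time-period, as they are extracting charts". R3 and R4 are blinded, and any unblinding is to be reported. Codes are assigned independently, disagreements go to consensus and then to the chief investigator, and kappa and percentage agreement are calculated. Limitations repeats that the first-stage reviewers are unblinded, because the papers identify the hospital.

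**The concern.** R3 and R4 see only charts that R1 and R2 have already classed as quality and safety. Table 4 has no eligibility item and no icon item, so no blinded step re-checks the three Table 3 codes. Those codes set the full-chart denominator and every icon's contribution to both parts of the proportion.

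The safeguards deal with disagreement. Double coding, consensus and kappa do not reveal a lean shared by two coders who both know arm and period. The documents do not say whether the chief investigator is blinded when settling disputes. Icon uniqueness has written rules. Chart eligibility is a yes/no item resting on a term that the documents do not define.

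At stake is a between-arm difference, reported with a 95% confidence interval, that could include some coding error related to arm.

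**Working it through.** **1. Trace of the main outcome**

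| Code | Table | Coded by | Blind? | Enters |
|---|---|---|---|---|
| Chart is quality/safety | 3 | R1, R2 | No | Decides which full charts count |
| Icon is quality/safety | 3 | R1, R2 | No | Decides which icons can count |
| Icon is unique | 3 | R1, R2 | No | Numerator and denominator |
| Full chart is SPC | 4 | R3, R4 | Yes | Numerator |

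**2. Does the stated reason cover all three unblinded codes?** It covers extraction, which is done from identifiable papers. It does not cover chart eligibility, because Step 2 already produces redacted chart images for two blinded coders. It partly covers icon uniqueness, which depends on what else is on the page.

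**3. Inputs for size.** The 10% and 40% come from Sample size calculation. That section's minimum of 16 hospitals reproduces: 38 per arm (two-sided, continuity-corrected) × (1 − 0.90²) = 38 × 0.19 = 7.22, so 8 per arm. Without the correction it is 32 × 0.19 = 6.08, so 7 per arm and 14 in total. This is background only. The documents give no error rates, chart counts or icon counts, so the rates below are assumptions.

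**4. Formulas.** Take 100 indicated charts with *s* SPC items and error rate *e*, in one direction, surviving consensus, in intervention post papers only.

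- Eligibility (share *e* of non-SPC charts wrongly dropped): *s* / [*s* + (100 − *s*)(1 − *e*)]
- Icons (*k* non-unique icons per SPC item, share *e* wrongly counted as unique): (*s* + *kse*) / (100 + *kse*)

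At *e* = 10%:

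- *s* = 10: eligibility 10/91 = 11.0%; icons 11/101 = 10.9% (*k* = 1) or 12/102 = 11.8% (*k* = 2).
- *s* = 40: eligibility 40/94 = 42.6%; icons 44/104 = 42.3% (*k* = 1) or 48/108 = 44.4% (*k* = 2).

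Shift in percentage points:

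| Route | True 10%, *e* = 5 / 10 / 20% | True 40%, *e* = 5 / 10 / 20% |
|---|---|---|
| Eligibility | 0.5 / 1.0 / 2.2 | 1.2 / 2.6 / 5.5 |
| Icons, *k* = 1 | 0.4 / 0.9 / 1.8 | 1.2 / 2.3 / 4.4 |
| Icons, *k* = 2 | 0.9 / 1.8 / 3.5 | 2.3 / 4.4 / 8.3 |

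The error can also run the other way. Wrongly dropping 10% of SPC charts at 40% gives 36/96 = 37.5%, a fall of 2.5 points.

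**5. What the design already removes** (eligibility route, *e* = 10%)

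- *Lean by period alone.* Post papers in both arms shift alike. With no true effect, 11.0 − 11.0 = 0. At 40% against 10%, 42.6 − 11.0 = 31.6, so 1.6 points remain.
- *Constant lean by arm.* Pre and post papers in that arm shift alike. With no true effect, subtracting baseline leaves 0. With a regression slope of 0.90 (the plan's correlation, assuming equal pre and post variances), 1.0 − 0.90 × 1.0 = 0.1 point remains.

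What remains is mainly a lean specific to one arm's post papers.

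**The case against.** The best defence is that this is a disclosed and reasoned choice. The protocol says twice that the first reviewers are unblinded, and Table 3 says openly that a unique icon enters both counts. Both arms supply pre and post papers, so much arm- or period-related leaning cancels. The study targets 30 points, against which one or two points is little. Blinding would also be incomplete. R1 and R2 would still extract and R1 would still redact. R3 and R4 would judge eligibility with the chart's format in view: if they dropped 10% of non-SPC charts in both arms, a true 30 points would still read 31.6, against 32.6 when only the intervention arm is affected. The documents also do not show that every chart's eligibility can be judged off the page.

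Most of this stands, and it limits the point to a minor one. It does not answer why chart eligibility is left to unblinded coders when redacted charts already go to blinded ones. Nor does Limitations say which parts of the main outcome the unblinded stage sets. Under no true effect, blind coding would remove the arm-specific error in that code.

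A reader might also infer that icon miscoding could produce the whole design effect. With an assumed 20, 30 or 40 full charts per paper at 10% SPC, adding 10, 15 or 20 unique icons brings the proportion to 40%. That shows how much weight icons carry. It does not show error, because that many icons would have to be wrongly counted in each paper despite explicit uniqueness rules.

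**Conclusion.** The tracing holds: one of the four main-outcome codes is assigned blind and three are not. The exposure is a lean shared by R1 and R2 that is specific to one arm's post-period papers. Its size and direction are unknown and it is probably modest. At an assumed 10% error the shift is 1.0 point (eligibility) or 0.9 to 1.8 points (icons) with no true effect, and 2.3 to 4.4 points at 40%. These figures rest on assumed error rates, one direction of error, and one or two non-unique icons per SPC item.

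A reader might infer that the result will be biased in favour of training, or that any coding difference by arm or by period distorts it. The documents support neither. They give no error rates, error can go either way, and the parallel arms with baseline adjustment absorb much of a period-only or constant arm lean. Nor is this concealment, since the unblinded stage is disclosed. The point is a minor, cheap improvement.

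**What to change.** 1. **Chart eligibility.** R1 and R2 extract all charts without filtering on quality and safety. R1 sends all of them redacted, with the measure name left visible, to R3 and R4, who code quality and safety status blind alongside SPC status. Add a written definition of a quality or safety measure. Any chart that cannot be judged without page context is flagged and settled under that definition.
2. **Icons.** Leave icon eligibility and uniqueness with R1 and R2 under the existing rules, and state in Limitations that these parts of the main outcome are coded unblinded. Blinding here would work poorly: uniqueness needs the page, and icons are taught in the training.
3. **Supportive analysis.** Pre-specify a repeat of the main analysis on full charts alone, reported by arm and period with the icon share. Say in advance that a smaller effect there could arise because icons let analysts show fewer full charts (Intervention section), so it would not by itself indicate coding bias.

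**Cost.** No new staff are needed: the same four reviewers and 40 papers, with more redaction and coding, and one extra analysis. The hours cannot be sized because the documents give no chart counts. Extraction and redaction remain unblinded.
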